## NUMBER OF PARTICIPANTS

Overall, a target of approximately 40,000 adult participants ( $\geq 18$ - to  $< 60$ -year-old and  $\geq 60$ -year-old, with and without relevant comorbidities) will be randomly assigned in this study. Efforts will be made to ensure good representation in terms of race, ethnicity, and gender.

It is intended that a minimum of approximately 30% of recruited participants will be  $\geq 60$  years of age and approximately 20% of recruited participants will be  $\geq 18$  to  $< 40$  years of age.

## INTERVENTION GROUPS AND DURATION

Participants will be vaccinated at the study site according to the schedules detailed above:

- Ad26.COV2.S supplied at a concentration of  $1 \times 10^{11}$  vp/mL in single-use vials, with an extractable volume of 0.5 mL, and dosed at  $5 \times 10^{10}$  vp
- Placebo: 0.9% sodium chloride (NaCl) solution

For blinding purposes, all participants will receive Ad26.COV2.S or placebo at Day 1 of the double-blind phase, using the same volume (ie, 0.5 mL). At the Month 6/Unblinding Visit, all placebo participants who have signed a new ICF will receive a single dose of Ad26.COV2.S, using the same dose level and the same volume (ie,  $5 \times 10^{10}$  vp per 0.5 mL). At the Year 1/Booster Visit, all participants who are eligible for booster vaccination, desire to receive a booster vaccination, and have signed a new ICF will receive a single dose of Ad26.COV2.S, using the same dose level and the same volume (ie,  $5 \times 10^{10}$  vp per 0.5 mL) as used for the primary regimen.

## EFFICACY EVALUATIONS

Up to Amendment 7, identification and molecular confirmation of SARS-CoV-2 infection and symptomatic COVID-19 will be performed throughout the study.

The occurrence of COVID-19-related hospitalization and COVID-19-related complications (such as but not limited to hyperinflammatory syndrome, pneumonia, neurological or vascular complications, severe

neurological or vascular events, acute respiratory distress syndrome, renal complications, sepsis, septic shock, death)a will be monitored throughout the study.

For the primary objective, all moderate to severe/critical COVID-19 cases will be considered.

As a secondary objective, VE in the prevention of asymptomatic SARS-CoV-2 infection and mild COVID-19 will be analyzed. For samples collected prior to implementation of Amendment 7: An immunologic test for SARS-CoV-2 seroconversion (ELISA and/or SARS-CoV-2 immunoglobulin assay) based on SARS-CoV-2 N protein, may be performed to identify cases of asymptomatic infection. This assay will be performed on samples obtained at Day 1 (pre-vaccination), Day 29, Day 71, Month 6 /Unblinding Visit, Year 1, and Month 18.

## IMMUNOGENICITY EVALUATIONS

Up to Amendment 7, blood will be collected from all non-Immunogenicity Subset (double-blind phase) participants for humoral immunogenicity assessments at Day 1 (pre-vaccination), Day 29, Day 71, Month 6/Unblinding Visit, and Year 1.

For a total of approximately 400 participants in the Immunogenicity Subset (ie, 400 participants at sites with access to appropriate processing facilities), blood will be collected for analysis of humoral immune responses at Day 1 (pre-vaccination), Day 29, Day 71, Month 6/Unblinding Visit, Year 1, Month 18, and Year 2 visit after double-blind vaccination, and additionally 28 days and 72 days after booster vaccination, if applicable.

Note: Those participants in the Immunogenicity Subset that transfer to the Homologous Booster Subset at the Year 1/Booster Visit (see below) will from that visit onwards follow the humoral immunogenicity sample schedule of the Homologous Booster Subset and discontinue the schedule of the Immunogenicity Subset.

Up to Amendment 7, for participants with suspected or confirmed COVID-19 (ie, meeting prespecified criteria on COVID-19 Day 1-2 and Day 3-5 and/or a SARS-CoV-2 positive sample on COVID-19 Day 1-2 or Day 3-5), blood will be collected on COVID-19 Day 3-5 and on COVID-19 Day 29 for immunogenicity assessments, including the assays summarized in the table below. As from Amendment 7, active follow-up will no longer be pursued and blood sampling for this purpose will no longer be performed.

## Booster Vaccination

Up to Amendment 7, blood will be collected from all non-Subset participants who received booster vaccination for humoral immunogenicity assessments at the Year 1/Booster Visit and 28 days, 72 days, and 6 months after booster vaccination. A blood sample for transcriptomics will be collected from all participants 28 days after booster vaccination.

Homologous Booster Subset: The Homologous Booster Subset will include approximately 200 participants. This subset will include participants from the Immunogenicity Subset, who received Ad26.COV2.S in the double-blind phase or after cross-over, and subsequently received an Ad26.COV2.S booster vaccination in the study. This group may be augmented by other participants to replace participants who are not available. Participants in the Homologous Booster Subset will have a blood sample collected pre-booster vaccination, and 28 days, 72 days, 6 months, and 1 year post booster vaccination for humoral immunogenicity assessment.

a World Health Organization (WHO). Clinical management of severe acute respiratory infection (SARI) when COVID-19 is suspected. Interim guidance, 13 March 2020. <https://www.who.int/docs/default-source/coronavirus/clinical-management-of-novel-cov.pdf>. Accessed 12 May 2020.

**Heterologous Booster Subset:** The Heterologous Booster Subset will include approximately 400 participants. This subset will include participants in the study who received placebo in the double-blind phase and have received primary vaccination with an mRNA vaccine or another authorized COVID-19 vaccine including protein, inactivated, and adenovector based vaccines outside the study, who subsequently remained in the study and subsequently received an Ad26.COV2.S booster vaccination in the study. Participants who already received an additional COVID-19 vaccination after the primary regimen outside the study will not be included in the Heterologous Booster Subset. Participants will be selected out of countries where these vaccines were authorized for emergency use or are licensed. Participants in the Heterologous Booster Subset will have blood collected pre-booster vaccination, and 28 days, 72 days, 6 months, and 1 year post booster vaccination for humoral immunogenicity assessment.

Additionally, approximately the first 60 eligible participants once operationally feasible of the Homologous Booster Subset and approximately the first 60 eligible participants once operationally feasible of the Heterologous Booster Subset will have blood collected pre-booster and 1 day and 28 days post booster vaccination for transcriptomics and cytokine/chemokine assessment.

#### Immunogenicity and Transcriptomic Assays

Humoral Assays	Purpose
Supportive of Secondary Objectives	
SARS-CoV-2 binding antibodies to S protein (ELISA)	Analysis of antibodies binding to SARS-CoV-2 S protein
SARS-CoV-2 seroconversion based on antibodies to N protein (ELISA and/or SARS-CoV-2 Immunoglobulin assay)	Analysis of antibodies binding to SARS-CoV-2 N protein
Supportive of Secondary and Exploratory Objectives	
SARS-CoV-2 neutralization (VNA)	Analysis of neutralizing antibodies against SARS-CoV-2 original strain and/or variants, using a live VNA and/or pseudovirion expressing S protein neutralization assay
SARS-CoV-2 binding antibodies to S protein (MSD)	Analysis of antibodies binding to the original and/or variants SARS-CoV-2 S protein (different than the assays supportive of the secondary objectives) and the receptor-binding domain (RBD) of SARS-CoV-2 S protein
Functional and molecular antibody characterization	Analysis of antibody characteristics including, but not limited to, avidity, crystallizable fragment (Fc)-mediated viral clearance, Fc characteristics, immunoglobulin (Ig) subclass, IgG isotype, antibody glycosylation, and assessment of antibody repertoire
Adenovirus neutralization (VNA)	Adenovirus neutralization assay to evaluate neutralizing antibody responses against the Ad26 vector
Binding antibodies to other coronaviruses (MSD)	Analysis of antibodies binding to coronaviruses other than SARS-CoV-2
Cytokine profiling	Analysis of cytokines, chemokines, and other proteins of the innate or adaptive immune response in the serum or plasma
Transcriptomic Assay	Purpose
Supportive of Exploratory Objectives	
Gene expression analysis	Analysis of gene expression by RNA transcript profiling in unstimulated cells or whole blood

Ad26 adenovirus type 26; ELISA enzyme linked immunosorbent assay; Fc crystallizable fragment; Ig(G) immunoglobulin (G); MSD Meso Scale Discovery; N nucleocapsid; RBD receptor binding domain; RNA ribonucleic acid; S spike; SARS CoV 2 severe acute respiratory syndrome coronavirus 2; VNA virus neutralization assay.

In areas where seroprevalence is predicted to be high, a screening serologic test for past or current infection with SARS-CoV-2 may be performed (in a local laboratory), at the discretion of the sponsor, to restrict the proportion of seropositive participants in the study. This does not apply to the open-label phase of the study.

A serologic test for past or current infection with SARS-CoV-2 may be performed for all participants at Day 1 (pre-vaccination), Day 29, Day 71, Month 6/Unblinding Visit, Year 1/Booster Visit (prior to vaccination, if applicable), Year 1 + 28 days for participants who received booster vaccination, Year 1 + 72 days for participants who received booster vaccination, and Month 18 (24 weeks after Year 1 Visit). Samples for the serologic tests will be sent to a central laboratory for testing.a Participants who test positive will be informed of the result by the study staff.

## SAFETY EVALUATIONS

The first 2,000 participants in each of the 2 age groups will remain under observation at the study site for at least 30 minutes post-vaccination to monitor for the development of acute reactions. If at the time of the Day 3 safety review of the initial 2,000 participants no acute reactions have been observed in the age groups, the observation period at the study site may be reduced to at least 15 minutes post-vaccination for the remaining participants in the study.

For all participants (throughout the study regardless of any protocol amendment):

- (S)AEs that are related to study procedures or that are related to non-investigational sponsor products will be reported from the time a signed and dated informed consent form (ICF) is obtained until the end of the study/early withdrawal.
- Clinically relevant medical events not meeting the above criteria and occurring between signing of the ICF and moment of vaccination in the double-blind phase of the study will be collected on the Medical History electronic case report form (eCRF) page as pre-existing conditions. This does not apply to the open-label phase.
- All SAEs and all AEs leading to study discontinuation (regardless of the causal relationship) are to be reported from the moment of vaccination until completion of the participant's last study-related procedure, which may include contact for safety follow-up. The sponsor will evaluate any safety information that is spontaneously reported by an investigator beyond the time frame specified in the protocol.
- MAAEs are defined as AEs with medically-attended visits including hospital, emergency room, urgent care clinic, or other visits to or from medical personnel for any reason. Routine study visits will not be considered medically-attended visits. New onset of chronic diseases will be collected as part of the MAAEs. MAAEs are to be reported for all participants from the moment of each vaccination until 6 months after the vaccination (applicable for both the double-blind and open-label phases of the study), except for MAAEs leading to study discontinuation which are to be reported during the entire study.
- Special reporting situations, whether serious or non-serious, will be recorded from the time of each vaccination until 28 days post-vaccination (applicable for both the double-blind and open-label phases of the study).
- Suspected AESIs (thrombotic events and thrombocytopenia [defined as platelet count below 150,000/ $\mu$ Lb]) will be reported from the moment of vaccination until the end of the study/early

a Vaccination with Ad26.COV2.S may interfere with some serologic assays utilized at local community health clinics/commercial laboratories, by seeking and identifying the spike protein in the vaccine and rendering a false positive result. For this reason, participants will be encouraged to not seek testing outside the study. If a participant requires testing outside of the protocol-mandated testing schedule, the site will guide them on the appropriate assay that identifies the viral nucleocapsid protein (and not the spike protein).

b Updated Proposed Brighton Collaboration process for developing a standard case definition for study of new clinical syndrome X, as applied to Thrombosis with Thrombocytopenia Syndrome (TTS). 18 May 2021. <https://brightoncollaboration.us/wp-content/uploads/2021/05/TTS-Interim-Case-Definition-v10.16.3-May-23-2021.pdf>. Accessed: 02 September 2021.

withdrawal. An AESI Adjudication Committee with appropriate expertise will be established to evaluate each suspected AESI and determine whether it is a case of thrombosis with thrombocytopenia syndrome (TTS). From the time of local approval of protocol Amendment 5 onwards, TTS is considered an adverse event of special interest (AESI).

- All AEs will be followed until resolution or until clinically stable.

As of Amendment 7, for all participants:

- Active follow-up of suspected COVID-19 episodes will be replaced by passive surveillance: during follow-up calls by the site at Month 18 and Month 24, new COVID-19 participant-reported events are to be reported as SAEs, AE or MAAEs.
- Concomitant medications for these events should be reported.
- If a COVID-19 confirmatory laboratory or assay read-out is available, this should be reported in the eCRF (self-reported or as part of CIOMS form).

For participants in the Safety Subset (double-blind phase):

- Solicited AEs, collected through an e-Diary, will be recorded from the time of vaccination until 7 days post-vaccination.
- All other unsolicited AEs, whether serious or non-serious, will be recorded from the time of vaccination until 28 days post-vaccination.

Up to Amendment 7: For participants who received booster vaccination at the Year 1/Booster Visit:

- Solicited AEs, collected through an e-Diary, will be recorded from the time of vaccination until 7 days post-vaccination. All participants will collect signs and symptoms in the e-Diary, if feasible. For a subset of participants, ie, participants included in the Safety Subset of the double-blind phase and all participants who previously received a heterologous COVID-19 vaccination outside the study, the e-Diary will be reviewed by the study personnel and solicited AEs recorded in the eCRF, if feasible. All other unsolicited AEs, whether serious or non-serious, will be recorded from the time of vaccination until 28 days post-vaccination for all participants.

As of Amendment 7, solicited and unsolicited AE reporting will stop for all participants.

## STATISTICAL METHODS

Note: The below is only applicable to the double-blind phase of the study unless mentioned otherwise.

### Sample Size Calculation

#### *Efficacy (Total Sample Size)*

The study target number of events (TNE) is determined using the following assumptions:

- a VE for molecularly confirmed, moderate to severe/critical SARS-CoV-2 infection of 60%.
- approximately 90% power to reject a null hypothesis of  $H_0: VE \leq 30\%$ .
- type 1 error rate  $\alpha = 2.5\%$  to evaluate VE of the vaccine regimen (employing the sequential probability ratio test [SPRT] to perform a fully sequential design analysis; detailed in the methods section).
- a randomization ratio of 1:1 for active versus placebo.

Events for the co-primary endpoints are defined as first occurrence of molecularly confirmed, moderate to severe/critical COVID-19 according to the case definition (see above) in the Per-protocol Efficacy

population at least 14 days after double-blind vaccination (Day 15) and at least 28 days after double-blind vaccination (Day 29) with study vaccine.

Under the assumptions above, the TNE to compare the active vaccine versus placebo equals 154, based on events in each active vaccination and placebo group, according to the primary endpoints case definition of moderate to severe/critical COVID-19.

If the primary hypotheses testing is successful, secondary objectives will be evaluated against a null hypothesis employing a lower limit  $VE > 0\%$ . The method to perform hypothesis testing of primary and secondary objectives preserving the FWER will be specified in the SAP. The FWER will be controlled at 2.5%.

Further details on the sample size calculation are provided in the body of the protocol.

The operating characteristics of the study design, statistical methods, study monitoring rules and efficacy evaluation specified in this protocol with the chosen event and sample sizes will be described in a separate modeling and simulation report and will be added to the SAP before the first participant is vaccinated.

No additional participants will be recruited for the open-label phase.

#### ***Immunogenicity Correlates (Correlates Subset)***

Correlates will be assessed in a subset where immune responses and transcriptome modifications are measured in all vaccine recipients who experience a SARS-CoV-2 event, and in random samples of vaccine recipients who have not been infected, in a 1:5 ratio. The goal of this case-control study is to assess correlates of risk of SARS-CoV-2 infection (and potential other secondary endpoints) in the vaccine group by comparing vaccine-induced immune responses and transcriptome modifications associated with COVID-19. Also, placebo participants will be included in this subset (placebo infected, seropositive [based on N protein] non-infected and seronegative non-infected), if feasible.

#### ***Safety (Safety Subset)***

Solicited and unsolicited AEs will be captured only in the Safety Subset, ie, approximately 6,000 participants (~3,000 from the active group, ~3,000 from the placebo group; and including at least 2,000 from the older age group [ $\geq 60$  years of age] if feasible).

#### **Populations for Analysis Sets**

For purposes of analysis, the following populations are defined:

- **Full Analysis Set (FAS):** All randomized participants with a documented study vaccine administration, regardless of the occurrence of protocol deviations and serostatus at enrollment. Analyses of safety will be performed on the FAS. Vaccine efficacy analyses can be repeated using the FAS.
- **Safety Subset:** subset of the FAS for the analysis of solicited and unsolicited AEs.
- **Per-protocol Efficacy (PP) population:** Participants in the FAS who receive study vaccine and who are seronegative at the time of vaccination and who have no other major protocol deviations that were judged to possibly impact the efficacy of the vaccine. Participants who became aware of their study vaccine allocation will cease to be part of the PP population. The PA of VE will be based on the PP population. The PP will be the main analysis population for efficacy analyses.
- **Per-protocol Immunogenicity (PPI) population:** All randomized and vaccinated participants, including those who are part of the Immunogenicity Subset and for whom immunogenicity data are available, excluding participants with major protocol deviations expected to impact the immunogenicity outcomes. In addition, for participants who experience a SARS-CoV-2 event

(molecularly confirmed), samples taken after the event and samples taken outside protocol windows will not be taken into account in the assessment of the immunogenicity. The PPI population is the primary immunogenicity population. For key tables, sensitivity immunogenicity analyses will also be performed on the FAS, including participants who are part of the Immunogenicity Subset for whom immunogenicity measures are available. Excluded samples might be taken into account as well in the sensitivity analysis. Analyses of vaccine immunogenicity and immune correlates of risk will be based on PPI.

The populations for the open label cross-over, booster and passive follow-up phase are described in the SAP. The list of major protocol deviations to be excluded from the efficacy for the double-blind analysis and/or immunogenicity analyses will be specified in the SAP and/or this list will be reported into the protocol deviation dataset of the clinical database before unblinding.

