To evaluate safety in terms of serious adverse events (SAEs) adverse events of special interest (AESIs) (during the entire study), medically-attended adverse events (MAAEs; until 6 months after double-blind or open-label vaccination), and MAAEs leading to study discontinuation (during the entire study) for all participants	Occurrence and relationship of SAEs and AESIs (during the entire study), MAAEs (until 6 months after [double-blind or open-label] Ad26.COV2.S), and MAAEs leading to study discontinuation (during the entire study) for all participants following vaccination
In a subset of participants, to evaluate the safety and reactogenicity in terms of solicited local and systemic adverse events (AEs) during 7 days after double-blind vaccination, and in terms of unsolicited AEs during 28 days after double-blind vaccination	Occurrence, intensity, duration, and relationship of solicited local and systemic AEs during the 7 days following vaccination and of unsolicited AEs during the 28 days after double-blind vaccination

Objectives	Endpoints
Immunogenicity	
In a subset of participants, to evaluate the immunogenicity of Ad26.COV2.S, as compared to placebo	Analysis of antibodies binding to the SARS-CoV-2 S protein by ELISA

a Molecularly confirmed COVID-19 is defined as a positive SARS-CoV-2 viral RNA result by a central laboratory using a RT-PCR based or other molecular diagnostic test.

b Per case definition for moderate to severe/critical COVID-19 as determined by the Clinical Severity Adjudication Committee (see below).

c Per case definition for mild COVID-19 as determined by the Clinical Severity Adjudication Committee (see below).

d Per US FDA harmonized case definition for COVID-19 (see below).

e All secondary efficacy endpoint analyses will occur in the per-protocol (PP) analysis set, in seronegative participants unless otherwise indicated in the Statistical Analysis Plan (SAP).

f For more information and the definition of the BOD endpoint, refer to the body of the protocol.

Exploratory objectives and endpoints, including correlates of protection, durability of protection, immunogenicity, and evaluation of efficacy in seropositive participants and/or participants with a SARS-CoV-2 positive RT-PCR or molecular test result, are included in the body of this protocol.

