**AND**

- has a SARS-CoV-2 positive RT-PCR or molecular test result from any available respiratory tract sample (eg, nasal swab sample, sputum sample, throat swab sample, saliva sample) or other sample

a Until Amendment 7, participants will be asked to undertake the COVID-19 procedures until 14 days after symptom onset (COVID-19 Day 15) or until **resolution of the COVID-19 episode**, whichever comes last (see Section 8.1.2).

OR

- develops a positive serology (non-S protein) test

Then, the participant will be considered to have experienced asymptomatic or undetected COVID-19.

Cases will be classified as being an "Asymptomatic SARS-CoV-2 infection" by the Clinical Severity Adjudication Committee utilizing the following guidelines as applicable, which are described in more detail in the charter for the committee.

- The definition of any case that is either RT-PCR positive that was previously RT-PCR negative or seropositive for N protein specific antibodies that was previously seronegative for N protein specific antibodies and is clinically asymptomatic will be considered as an asymptomatic COVID-19 case.
- The definition of clinically asymptomatic COVID-19 is defined as no clinical symptoms that would be classified as mild, moderate, or severe COVID-19 by the protocol case definition for symptoms independent of the SARS-CoV-2 N protein specific antibody seroconversion or RT-PCR results.

Potential asymptomatic cases that are identified by N protein specific SARS-CoV-2 seroconversion will all be examined by the Clinical Severity Adjudication Committee for the presence of any signs or symptoms and if found, to determine if they would still be classified as asymptomatic COVID-19. Cases which are moderate, severe, hospitalized, or fatal that are found by SARS-CoV-2 N protein specific antibody seroconversion will be utilized in a sensitivity analysis to determine, if any conclusions would be changed by adding to the primary case definition of a positive RT-PCR with appropriate signs and symptoms to those cases which were identified by SARS-CoV-2 N protein specific antibody seroconversion with appropriate signs and symptoms.

As of Amendment 7, severity assessment by the CSAC may still be performed and will be based on the data collected through the passive follow-up (eg, hospitalization reported in the context of SAEs). The scope of the severity review may change and will be described in the charter.

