- l. From the moment the ICF for Amendment 7 is signed, the participant moves to the passive surveillance phase schedule. COVID-19 is to be reported as SAE, AE, or MAAE until study end (see Section 8.3.1 for the reporting of COVID-19 events as of protocol amendment 7). Participants may contact the site at any time in between scheduled visits to report COVID-19 episodes.

- m. Refer to Section 6.10 for collection and recording of concomitant therapies associated with SAEs, solicited and unsolicited AEs, suspected AESIs, and MAAEs and new COVID-19 (S)AEs or COVID-19 MAAEs.
- n. Whole blood samples will be used for a complete blood count, including platelets, in a local laboratory or a substitute for local laboratory, depending on local feasibility towards turnaround time of sample processing. Serum samples will be derived from the whole blood sample and stored for potential future coagulation-related testing in a central laboratory if the participant experiences a suspected AESI (see Section 10.2, Appendix 2).
- o. Blood samples for immunogenicity will only be taken if the early exit visit is at least 10 days after the previous immunogenicity blood draw.
- p. Blood sample for humoral immunity at Year 1/Booster Visit (prior to booster vaccination), Month 18, and Year 2, and additionally 28 days and 72 days after booster vaccination, if applicable, may also include sample for sero-confirmation of SARS-CoV-2 infection. Samples will be collected for 400 participants at selected sites.
- q. Blood sample for humoral immunity at the Year 1/Booster Visit (pre-vaccination) and 28 days, 72 days, 6 months, and 1 year after booster vaccination, may also include sample for sero-confirmation of SARS-CoV-2 infection. Samples will be collected for 600 participants at selected sites.
- r. The approximate blood volume collected depends on which one of the immunogenicity or booster subgroups the participant is in.
- s. No further booster doses will be administered under protocol amendment 7, except if there was a medical reason that prevented a participant to receive the Ad26COV2.S vaccine prior to acceptance of amendment 7 or if there is a non-availability of other vaccines to the participant. The investigator should inform participants on the availability of other COVID-19 vaccines.

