### 1.3.4. Participants With (Suspected) COVID-19

#### 1.3.4.1. Passive Follow-up (As of Amendment 7)

As of Amendment 7, active follow-up of suspected COVID-19 episodes will be replaced by a passive follow-up approach.

New suspected COVID-19 episodes will be participant-reported and will not include any laboratory sampling. Site staff will collect information on the new COVID-19 episodes at scheduled time points and report these as SAEs, AEs, or MAAEs, as applicable. Participants may contact the site at any time in between scheduled visits to report COVID-19 episodes. Concomitant therapies related to these events are to be reported, as well as any confirmatory COVID-19 laboratory information, if available.

Guidance on (S)AE coding may be provided.

Some participants will have an ongoing COVID-19 event at time of signing the informed consent of protocol amendment 7. Also, under protocol amendment 7, the eCOA will be decommissioned. Hence participant will stop using the eCOA as of the consent visit. The outstanding activities planned for the follow-up of COVID-19 events will also end on that date for the participants (eg no further samples, no MRU completion, no MA-COV completion, no further visit in the context of the COVID-19 follow-up). The eCOA will be stopped based on approval of protocol Amendment 7 at each study site.

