### 3.3. Open-label Passive Follow-up Phase

With Amendment 7, the active follow up of suspected COVID-19 episodes is replaced by a passive follow-up. Participants will enter this phase on the day of consenting to Amendment 7 (or with the stop of the eCOA at each study site, which ever comes first) until end of study.

In the passive follow-up phase, the same cohorts as from the booster phase are included, and all data will be descriptively presented by cohort depending on the vaccination schedule received during the follow-up phase. Since COVID-19 reporting changed from an active approach to a passive approach, the evaluations will be limited. Efficacy evaluations may be performed if feasible and will be described in the SAP as applicable.

The secondary and exploratory objectives and endpoints for the passive follow-up phase of the study are:

Objectives	Endpoints
The secondary safety objective of the double-blind phase (see double-blind objectives).	
 
The secondary safety endpoint of the double-blind phase (see double-blind endpoints).
 

Exploratory	
To evaluate COVID-19 in terms of (S)AEs MAAEs, hospitalizations and fatal AEs linked to COVID-19*	
 
SAEs and AEs linked to COVID-19
 
MAAEs linked to COVID-19
 
SAEs linked to COVID-19 that require hospitalization
 
Fatal AEs linked to COVID-19
 

In the immunogenicity subset of participants: to evaluate the immunogenicity of Ad26.COV2.S at available timepoints	
 
Analysis of antibodies binding to the SARS-CoV-2 S protein by ELISA
 

In the Heterologous and Homologous Booster Subsets: to compare the immune responses 28 days following booster dose administration	
 
Analysis of antibodies binding to the SARS-CoV-2 S protein by ELISA
 
Qualitative comparison of responses in terms of binding, neutralizing antibody against Wuhan reference strain and variants of interest utilizing wtVNA and/or psVNA, depending on feasibility.
 

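### The double-blind per-protocol immunogenicity rule drops samples only after molecularly confirmed infection, so infections seen only by N-seroconversion stay in the primary immunogenicity set

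*Protocol*

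**What the plan says.** The PPI population is defined in the Synopsis (section 1.1), Populations for Analysis Sets. It starts from randomized and vaccinated participants with immunogenicity data, "excluding participants with major protocol deviations expected to impact the immunogenicity outcomes". It has one infection rule: for participants with a SARS-CoV-2 event ("molecularly confirmed), samples taken after the event and samples taken outside protocol windows will not be taken into account". Footnote a to the double-blind objectives gives the meaning of molecular confirmation: "defined as a positive SARS-CoV-2 viral RNA result by a central laboratory".

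The same paragraph makes PPI the primary immunogenicity population and the basis for immune correlates of risk. It plans a sensitivity analysis on the full analysis set (FAS), in which excluded samples might be put back. The Synopsis section on immunogenicity analyses says that all of them use PPI, without formal testing.

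Infection is defined more widely elsewhere. Under the case definition for asymptomatic or undetected COVID-19, a participant without qualifying symptoms who "develops a positive serology (non-S protein) test" is considered to have had the infection. The secondary objectives include N-based seroconversion between Day 1, Day 29, Day 71 and the Month 6/Unblinding Visit. The Synopsis sections on efficacy and immunogenicity evaluations foresee N-serology at these visits, worded as something that may be done.

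**The concern.** Infection raises spike-binding and neutralising antibody, as vaccination does. A rule that removes post-infection samples exists to keep that second source out of the vaccine-response estimate. Here its trigger is narrower than the protocol's own definition of infection. Silent infections are the ones least likely to produce a swab and a central RNA result, and most likely to be recognised only by N-serology. If the N-assay is run as foreseen, the sponsor will know that certain samples are post-infection, and the rule as written still keeps them in the primary set.

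At stake is the description of the antibody response by arm at Day 29, Day 71 and Month 6, and its consistency with the protocol's infection endpoints. No co-primary conclusion, type I error or power figure depends on it.

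**Working it through.** **Step 1. Can anything in the rule catch an N-only infection?** There are three routes out of the PPI set.
- The infection trigger needs central-laboratory RNA, which an N-only infection lacks by definition.
- The sampling-window trigger is unrelated to infection.
- The major-deviation list is left to the SAP or the deviation dataset, but acquiring an infection is not a protocol deviation.

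None of the three removes the sample.

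**Step 2. Does the sensitivity analysis catch it?** The FAS version may restore samples that PPI excluded. It moves towards more post-infection samples, and nothing in it removes seroconverters.

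**Step 3. Are the data there?** The schedule before Amendment 7 (section 1.3.3, footnotes cc and ee) says the humoral samples at Day 1, Day 29, Day 71 and Month 6 include a sample for sero-confirmation. The serum is drawn, and only running the N-assay is optional.

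**Step 4. Direction and size.** The protocol gives no figure to reproduce, so this is an illustration. Let p be the share of retained samples in an arm at a visit that follow an unrecognised infection, and k the fold-rise in titre that infection causes. Neither p nor k is in the documents; both are assumed. On the log scale the arm mean shifts by p × log k, so

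GMT multiplier = k^p.

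| p | samples affected if n = 400 | k = 5 | k = 10 |
|---|---|---|---|
| 5% | 20 | 5^0.05 = 1.08 | 10^0.05 = 1.12 |
| 10% | 40 | 5^0.10 = 1.17 | 10^0.10 = 1.26 |

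The 400 is the planned size of the whole Immunogenicity Subset. The column shows scale only, since p applies within an arm.

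For the vaccine/placebo contrast with a common k, the multiplier is k^(p_vaccine − p_placebo). Suppose p_placebo = 10%, vaccinees have 60% fewer such infections (p_vaccine = 10% × 0.4 = 4%), and k = 10. The ratio is then multiplied by 10^(0.04 − 0.10) = 10^(−0.06) = 0.87. With p_placebo = 5% and p_vaccine = 2% it is 10^(−0.03) = 0.93.

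Absolute levels move up in whichever arm is affected. The between-arm ratio moves down if placebo has more silent infection, and does not move if the shares and fold-rises are equal.

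**The case against.** The strongest objection is scope. A reader might infer that every infection during passive follow-up stays in the PPI set, hiding antibody waning at Month 18 and Year 2 and distorting booster responses. Three parts of the protocol invite that reading:
- From Amendment 7, "New suspected COVID-19 episodes will be participant-reported and will not include any laboratory sampling" (section 1.3.4.1).
- The passive phase still aims "to evaluate the immunogenicity of Ad26.COV2.S at available timepoints" (section 3.3).
- The subset footnotes p and q in section 1.3.2 say the sample "may also include sample for sero-confirmation of SARS-CoV-2 infection", and the seroconversion plan in the Synopsis opens "For samples collected prior to implementation of Amendment 7: An immunologic test for SARS-CoV-2 seroconversion".

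The protocol does not support that inference. The Synopsis statistical methods open by limiting themselves to the double-blind phase unless stated otherwise. The paragraph after the PPI definition leaves the cross-over, booster and passive-phase populations to the SAP. Recruitment to the booster subsets also closed with Amendment 7, so most 28-day post-booster samples precede passive follow-up. This objection stands, and the point is confined to the double-blind phase.

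A second tempting reading is that silent infection always flatters the vaccine. It does not, as the ratio calculation shows. A third is that the correlates analysis is necessarily contaminated. The Synopsis describes its non-case vaccinees as not infected and separates placebo non-cases by N-serostatus, so that does not follow.

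Active surveillance also limits the affected share before unblinding. Symptoms are checked at least twice weekly, any positive RT-PCR starts the COVID-19 procedures, and RT-PCR is done at Month 6. This argues for a small p, not for a sound rule. Finally, sections 8.1.4, 9.3 and 9.6 are not in the part of the protocol available here and should be checked for fuller handling.

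**Conclusion.** The point holds for the double-blind phase. The primary immunogenicity set keeps samples that the protocol's own infection definition would call post-infection, and the planned sensitivity analysis does not show what happens without them. The true size is unknown. Under the assumed p of 5–10% and k of 5–10, an arm's GMT is raised by a factor of about 1.1 to 1.3; the vaccine/placebo ratio may be lowered.

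Because immunogenicity is descriptive, this is a worthwhile, inexpensive correction and not a threat to the trial's main conclusions. For later phases the point is conditional: it matters only if the SAP reuses the same rule, in which case central RNA confirmation of new episodes would essentially no longer be available to trigger it.

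**What to change.** 1. In the PPI definition, also exclude samples taken at or after the first N-positive result that follows an N-negative sample. At minimum, add a sensitivity analysis that excludes them, alongside the FAS analysis already planned.
2. State that N-serology will be run on the Immunogenicity Subset samples used for immunogenicity, replacing the optional wording.
3. If the SAP carries the PPI rule into the cross-over, booster or passive phases, apply the same trigger there and add positive tests reported in the eCRF.

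The cost is a change of wording, N-assay runs on serum already drawn, and fewer evaluable samples. Reporting the number excluded by arm and visit would show how much information is lost.
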